#### 11.3.2 Efficacy Evaluable Population

The efficacy evaluable population includes all participants enrolled in the study who received the single BTX injection, underwent distal pancreatectomy/RAMPS, and had up to 30 days or greater of postoperative follow-up for POPF assessment. Participants who experience surgical delay greater than 6 weeks are not evaluable. All efficacy analyses will be conducted using the efficacy evaluable population. Safety analyses related to surgery will use the efficacy population.

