## **8.5 FOLLOW-UP**

Participants will be followed for 30 days following distal pancreas resection for efficacy. For safety, patients will be followed for 30 days following BTX injection if no surgery occurs or 30 days after surgery, whichever is longer. A follow-up visit will occur 14 days ( $\pm$  7 days)- following hospital discharge, consistent with standard of care practices. Additionally, all subjects will be contacted by phone by the NSQIP Surgical Clinical Reviewer ([name]) or other study team member approximately 30 days following operation to collect standard NSQIP other study datapoints. If a participant is diagnosed with any BTX-related adverse event (of any grade), additional follow-up phone calls will be performed monthly for three months following BTX injection to ensure resolution at the end of BTX duration of action.

Subjects not undergoing pancreatectomy and those undergoing pancreatectomy greater than 6 weeks from the date of BTX injection will not be evaluable for assessing efficacy of the study intervention but will be evaluable for assessing safety. The 6 weeks timepoint is chosen because the maximal efficacy of BTX may begin to wane following this timepoint. In patients undergoing BTX injection but not undergoing planned pancreatectomy (or experiencing a delay in pancreatectomy due to an AE from BTX), data on the reason(s) for delay or cancelled operation will be recorded.

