#### 11.4.4 SAFETY ANALYSES

Adverse events will be tabulated by the Medical Dictionary for Regulatory Activities (MedDRA Version 21.1) preferred term and system organ class. The severity of the AE will be assessed by National Cancer Institute (NCI) Common Terminology Criteria for Adverse Events (CTCAE) version 5.0. Using the safety analysis set, descriptive statistics will be used to summarize all on-study AEs, grade 3-4 AEs, treatment-related AEs, grade 3-4 treatment-related AEs, SAEs, treatment-related SAEs, and AEs leading to study therapy discontinuation. Grade 3-4 laboratory abnormalities will be summarized using worst grade NCI CTCAE v5.0 criteria.

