#### 11.4.5 PLANNED INTERIM ANALYSES AND STOPPING RULE

A safety-run in to test the endoscopic BTX injection technique will be performed. During the safety run-in, the PI will evaluate patient safety outcomes including grade 3 or higher adverse events. Additionally, the study will be evaluated by the DSMC following the completion of the first three participant's safety evaluation periods (30 days following BTX injection or 30 days following surgery, whichever is longer). Progressive study enrollment will continue throughout the safety run-in, and enrollment will be halted if recommended by the DSMC after completion of the run-in. If 2 or more of the first 6 participants enrolled experience delay in planned surgery  $\geq$  14 days (due to significant GI hemorrhage, perforation, or adverse reaction to BTX) or pancreatitis requiring hospitalization, then the study will be halted for safety. If 2 or more of the first 6 participants experience delay in planned surgery  $\geq$  14 days (due to significant GI hemorrhage, perforation, or adverse reaction to BTX) or pancreatitis requiring hospitalization, the study will be halted for safety. An analysis of adverse events will be performed, and if an alteration in the intervention technique or other prophylactic treatment cannot be identified the study will be terminated. If an alteration or prophylactic treatment can be found, the study will resume with an additional 6 patient safety run-in with identical stopping rules.

A futility analysis will be conducted based on the stopping rule of Simon's two-stage design after 25 Stage I participants have met the eligibility criteria for the efficacy evaluable population (defined in 11.3.2). All participants enrolled on stage 1 (n=25) will need to complete the study intervention, distal pancreas resection, and 30 days of follow up for postoperative pancreatic fistula before the interim analysis can be completed. Recruitment will be paused until interim analysis is completed. The trial will be terminated if there are 2 or more crPOPF among these 25 participants. If there are less than 2 crCOPF among these Stage I participants, the trial will continue and enroll 25 additional participants in Stage II. The treatment will be considered promising and deserving of further investigation if there are less than 3 crCOPF among the total of evaluable 50 participants.

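### Surgery-related safety summaries are assigned to the efficacy-evaluable set, so participants operated on late drop out of them and the status of early deaths is left open

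*Combined protocol and SAP*

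**What the plan says.** - **Set used for surgical safety.** Section 11.3.2 ends: "Safety analyses related to surgery will use the efficacy population".
- **Late surgery.** The same section adds: "Participants who experience surgical delay greater than 6 weeks are not evaluable". Section 8.5 starts the 6 weeks at the injection. It says that participants with no pancreatectomy, or with one after that limit, "will not be evaluable for assessing efficacy of the study intervention but will be evaluable for assessing safety".
- **Follow-up condition.** To be efficacy evaluable a participant must have "had up to 30 days or greater of postoperative follow-up for POPF assessment". Section 11.4.5 requires the Stage I participants to complete "30 days of follow up for postoperative pancreatic fistula before the interim analysis can be completed".
- **Main safety tables.** Section 11.4.4 reads: "Using the safety analysis set, descriptive statistics will be used to summarize all on-study AEs". Section 11.3.1 defines that set as all enrolled participants who received the injection.
- **Planned numbers.** The Synopsis and Section 11.2 plan for up to 55 injected participants, to give 50 evaluable.
- **A second window.** The note to the Schematic of Study Design keeps participants evaluable for efficacy only if surgery falls within 28 days of injection.

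**The concern.** Whether a participant belongs in a safety set should not depend on something the treatment may have caused. Here it can. Section 2.2 counts events that delay surgery within the safety endpoint, Section 10.2.2 makes a procedure-related complication that delays surgery a serious adverse event, and Section 11.4.5 builds a safety stopping rule partly on delay. A participant whose injection complication pushes surgery past 6 weeks, and who then has a difficult operation, would be missing from any summary of surgical safety.

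The follow-up condition raises a similar problem. If 30 completed days are required, loss to follow-up after surgery also removes a participant, and the plan gives no rule for someone who dies on, say, day 10.

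The same post-operative event could then appear in the Section 11.4.4 tables and be absent from a surgical summary. Since the plan does not list the surgery-related analyses, that choice is left to the analyst, possibly after the data are known. None of the defined sets consists of everyone injected and operated on, which is the natural denominator for surgical safety.

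**Working it through.** **Step 1: follow one participant through the sections.** Suppose surgery takes place 7 weeks (49 days) after injection.
- Section 8.5: not evaluable for efficacy, evaluable for safety.
- Section 11.3.2, with the clock starting at injection as in 8.5: outside the efficacy-evaluable set, so outside surgery-related safety analyses.
- Section 11.4.4: inside the safety set, so all recorded events are tabulated.

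Surgery on day 35 gives a different conflict: evaluable for efficacy under Sections 8.5 and 11.3.2 (35 is below 42 days), not evaluable under the Schematic (35 is above 28).

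**Step 2: is 30 days of follow-up a condition?** Read literally, the wording of 11.3.2 sets no minimum. Four other places point to one: the Synopsis (50 patients completing 30-day follow-up), Section 3.1 (50 completing intervention and follow-up), Section 11.2 (the drop-out allowance is labelled as lost follow-up) and Section 11.4.5. A 30-day minimum is the likely reading, but it is not explicit.

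**Step 3: deaths before day 30.** No section excludes them and none retains them. Section 5.4 only lists death beside loss to follow-up as a reason for leaving the study.

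**Step 4: how many participants.** The plan's figure is 50 × 1.10 = 55. Dividing instead gives 50 / 0.90 = 55.6, which makes no practical difference here. Outside the evaluable set: 55 − 50 = 5, and 5 / 55 = 9.1%. This is an upper figure for the present point, because those never operated on would be outside a surgical safety set in any case.

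**Step 5: what that could do to a surgical event rate.** The documents give no rate of major surgical complications and no count of late operations or early deaths, so what follows rests on assumptions. Let *a* of the 50 evaluable participants have an event. Let *m* operated participants lie outside the set (1 to 5), *k* of them with an event. The rate in all operated participants is (*a* + *k*) / (50 + *m*).

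| Efficacy set (assumed) | m=1, k=1 | m=3, k=3 | m=5, k=5 | m=5, k=0 |
|---|---|---|---|---|
| 5/50 = 10.0% | 6/51 = 11.8% | 8/53 = 15.1% | 10/55 = 18.2% | 5/55 = 9.1% |
| 10/50 = 20.0% | 11/51 = 21.6% | 13/53 = 24.5% | 15/55 = 27.3% | 10/55 = 18.2% |
| 15/50 = 30.0% | 16/51 = 31.4% | 18/53 = 34.0% | 20/55 = 36.4% | 15/55 = 27.3% |

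The rate rises only if *k*/*m* exceeds *a*/50. In the middle row with *m* = 5, one event among the five leaves it unchanged (11/55 = 20.0%).

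For post-operative deaths, if they were left out: one turns 0/50 (exact 95% CI 0 to 7.1%) into 1/51 = 2.0% (0.05 to 10.4%); two give 2/52 = 3.8% (0.5 to 13.2%).

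**The case against.** The best defence is that little is lost. Section 10.5 records grade 3 or higher events whatever their cause, until 30 days after injection or surgery, whichever is longer. Section 10.2.2 makes death and hospitalization serious events. Sections 11.4.2.1 and 11.4.4 analyse serious and other adverse events on the safety set. A reader might infer that the worst post-operative courses vanish from the trial's safety results. The documents do not support that, because recorded events after late surgery still reach the main tables. This part of the defence stands, and it limits the point to surgery-specific summaries. It does not make the choice of set sound, and Section 11.4.2.1 is itself unclear, since it names the safety set but speaks of participants who undergo resection.

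A second defence is that Sections 8.5 and 11.3.2 need not contradict each other. Section 8.5 covers never-operated participants in the same sentence, so its reference to safety may mean safety of the injection, which Section 11.3.1 puts on everyone injected. That reading is possible, so the two sections sit badly together rather than being in flat conflict. But participants operated on late do have surgical outcomes, and the reason given in 8.5 for the cut-off, waning of the toxin effect, concerns efficacy.

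A third is that major complications, drainage and re-operation are treated in Sections 9 and 11.4.3 as efficacy or exploratory outcomes, so changing one sentence would not touch them. This is correct, and it is why the fix must also name the analyses.

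**Conclusion.** The point holds in a limited form. Section 11.3.2 puts surgery-related safety on a set that excludes late operations, and so selects on a possible harm of the intervention. It probably also excludes participants with incomplete follow-up, and it is silent on early deaths. The effect is confined to surgery-specific safety summaries; the main adverse event tables are not affected.

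At most 5 of 55 injected participants (9.1%) are involved if the planned numbers are met. With an assumed 20.0% event rate in the evaluable set, the rate in all operated participants could lie between 18.2% and 27.3%, and both ends require all five to have been operated on. The upper end also requires all five to have had an event. That is extreme, since the plan budgets these participants as lost to follow-up rather than as late operations or deaths.

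Two stronger conclusions are tempting. One is that the plan excludes post-operative deaths; it does not say so, and the inference rests on silence and an unclear phrase. The other is that the bias must favour safety. Exclusion linked to harm makes that the likely direction, but late operations need not go worse, and leaving out event-free participants would raise the reported rate.

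**What to change.** Replace the sentence in Section 11.3.2 with wording to this effect: *Surgical safety will be summarised in all participants who were injected with BTX and had the pancreatectomy, whatever the interval between the two and however long the post-operative follow-up, including those who die before day 30.* Keep the efficacy-evaluable set for efficacy only.

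In the same amendment:
- List the analyses that count as surgery-related safety, and say whether major complications, drainage and re-operation are among them or remain purely exploratory efficacy outcomes.
- Replace the follow-up phrase in the efficacy-evaluable definition with a clear condition, and state how a death before day 30 is handled there.
- Clarify in Section 11.4.2.1 whether the denominator is everyone injected or only those operated on.
- Reconcile the evaluability windows: 28 days in the Schematic of Study Design, 6 weeks in Sections 8.5 and 11.3.2.

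The cost is a few sentences of text. Sections 8.5 and 10.5 already provide for collecting the data, so no extra participants or visits are needed.

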## 11.4 DESCRIPTION OF STATISTICAL METHODS

### 11.4.1 ANALYSIS OF PRIMARY ENDPOINT(S)

Using the efficacy analysis set, the estimate of clinically relevant POPF rate on pre-operative endoscopic BTX injection will be measured and reported with 95% exact confidence interval.

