	Preoperative endoscopy with Sphincter of Oddi BTX injection will be the only trial-related intervention for patients participating in this trial. All the other procedures, including assessment of laboratory parameters, belong to the standard perioperative and postoperative procedures performed in patients undergoing distal pancreatectomy. In patients with childbearing potential, a pregnancy test will be performed during the routine preoperative laboratory examinations.
Statistical Analyses	This is a single arm, open-label, Phase II study to estimate the rate of clinically relevant POPF in participants that receive pre-operative endoscopic BTX injection. Using a Simon's 2-stage, a total of 50 evaluable participants will achieve an 88% power to detect a difference in crPOPF rate of 9.2% (H0: $\pi = 0.112$ versus Ha: $\pi = 0.02$ ; with a one-sided alpha level of 0.05). The trial will be continued following stage 1 if there is one or fewer crPOPF among the first 25 participants. If the study proceeds to stage 2, a total of 50 participants will be evaluated towards the primary endpoint, and the intervention considered promising if there are two or fewer cases of crPOPF.

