### 11.2 SAMPLE SIZE DETERMINATION

This will use a Simon's two-stage design. The two-stage design to test a difference of 9.2% (2% vs. 11.2%) has an expected sample size of 30.33 and a probability of early termination of 0.787. If the pre-operative BTX injection is effective, there is a 0.124 probability of concluding that it is not, equivalently 0.876 power. After the pre-operative BTX injection on 25 patients in the first stage, the trial will be terminated if 2 or more crPOPF. If the trial goes on to the second stage, a total of 50 participants will be studied. If the total number crPOPF is less than 3, the drug will be considered efficacious. Anticipating 10% drop-out (lost follow-up), up to 55 participants need to be enrolled to achieve 50 evaluable participants. The sample size and power analysis were conducted using PASS 15 software (<http://www.ncss.com/software/pass/>).

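### The exact interval planned in Section 11.4.1 is not matched to the two-stage rule: a small effect, but at 2/50 the trial is called promising while every upper limit exceeds the 11.2% null

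*Combined protocol and SAP*

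**What the plan says.** The primary analysis in Section 11.4.1 is a single sentence: in the efficacy analysis set, the crPOPF rate "will be measured and reported with 95% exact confidence interval". It names no exact method, two-stage estimator, p-value or link to the decision.

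The decision is set elsewhere. Sections 11.2 and 11.4.5 stop the trial at 2 or more crPOPF among the first 25. After stage 2 the treatment is promising "if there are less than 3 crCOPF among the total of evaluable 50 participants" (the spelling is the plan's; crPOPF is meant). The Synopsis gives a null rate of 11.2%, an alternative of 2% and a test "with a one-sided alpha level of 0.05". Section 11.2 states that, if the treatment works, "there is a 0.124 probability of concluding that it is not, equivalently 0.876 power". It also says that the design "has an expected sample size of 30.33 and a probability of early termination of 0.787". No section gives the rule's attained type I error.

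On numbers, Section 11.2 says: "Anticipating 10% drop-out (lost follow-up), up to 55 participants need to be enrolled to achieve 50 evaluable participants". The final cut-off is given for 50 evaluable only.

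**The concern.** A Simon trial can end at 25 or at 50 participants, so its outcomes do not follow one binomial distribution with n = 50. An interval computed as if they did uses a different tail area from the rule. The two-sided 95% level adds a second mismatch, because it leaves 2.5% in the upper tail while the rule is stated at 5% in one tail.

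At the boundary result of 2/50, the report would call the treatment promising next to an interval that contains the historical rate, and the plan does not tell the reader how to weigh the two. If the evaluable number is not 50, neither the rule nor its error rate is defined.

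**Working it through.** **Inputs.** Null 0.112, alternative 0.02 and one-sided alpha 0.05 (Synopsis). Stage sizes 25 + 25, continue on 0–1 events, promising on 0–2 in total (Sections 11.2 and 11.4.5). Cap of 55 with 10% loss (Section 11.2). Assumption: the exact interval is Clopper-Pearson on X/50. Write b(x; n, p) for the binomial probability and B(x; n, p) for its cumulative sum.

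**1. The plan's own figures.**
- Early termination at 0.112: 1 − B(1; 25, 0.112) = 1 − (0.0513 + 0.1618) = 0.787. Stated 0.787.
- Expected N: 25 + 25 × 0.2132 = 30.33. Stated 30.33.
- Power at 0.02: b(0)·B(2) + b(1)·B(1), each with n = 25, = 0.6035 × 0.9868 + 0.3079 × 0.9114 = 0.876. Stated 0.876.

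All three reproduce.

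**2. Type I error of the same rule.** At 0.112: 0.0513 × 0.4581 + 0.1618 × 0.2132 = 0.0235 + 0.0345 = 0.0580, above the stated 0.05. At the 11.3% background rate in Section 1.1.1 it is 0.0557. It falls below 0.05 only for a null above about 11.57%.

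**3. Fixed-sample tail at 2/50.** B(2; 50, 0.112) = 0.0706. The excess over 0.0580 is the path with two events in stage 1 and none in stage 2: 0.2449 × 0.0513 = 0.0126. The design stops before that path can occur, so the fixed-sample calculation counts an impossible outcome.

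**4. Upper limits.** Each limit is the p at which the lower-tail probability equals 0.05 (one-sided 95%) or 0.025 (two-sided 95%). The two-stage tail orders results by stage; ordering by the unbiased estimate gives the same tails here.

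| Result | One-sided 95%, fixed | One-sided 95%, two-stage | Two-sided 95%, fixed | Two-sided 95%, two-stage |
|---|---|---|---|---|
| 0/50 | 5.8% | 5.8% | 7.1% | 7.1% |
| 1/50 | 9.1% | 9.1% | 10.6% | 10.6% |
| 2/50 | 12.1% | 11.6% | 13.7% | 13.2% |

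The first two rows agree because a total of 0 or 1 cannot pass through a stage-1 stop. In the third row all four limits exceed 11.2%. The matching one-sided p-values at 2/50 are 0.071 (fixed) and 0.058 (two-stage).

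**5. Coverage.** Under the two-stage design the fixed-sample 95% interval covered the true rate 96.4% to 99.2% of the time at seven rates from 1% to 15%.

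**6. Point estimate.** Over all outcomes the crude rate is biased upward: +0.30 percentage points at a true 2%, +0.88 at 5% and +0.87 at 11.2%. The uniformly minimum-variance unbiased estimate (UMVUE) at 2/50 averages x/25 over the permitted stage-1 counts x = 0 and 1. Those counts have 300 and 625 arrangements, so it is (625/25)/(300 + 625) = 25/925 = 2.7%, against a crude 4.0%. Among trials that reach stage 2 both estimates are low. At a true 5% the mean crude rate is 3.6% and the mean UMVUE 2.3%; at 11.2% they are 7.1% and 3.0%.

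**7. Evaluable number.** With independent losses of 10%, P(Bin(55, 0.9) ≥ 50) = 0.52. The same calculation gives 0.94 at 5% loss and 0.15 at 15%. If the cut-off of 2 were kept with 47 evaluable (25 + 22), the two-stage type I error at 0.112 would be 0.073.

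**The case against.** The strongest reply is that the omission does little harm. The interval differs from a two-stage one at only one of the three results called promising. There it is wider on the upper side, which is cautious for an efficacy claim, and it does not undercover at the rates checked. The plan also never uses the interval as a test: Section 11.4.5 decides by count, so different tail areas are not in themselves an error. All of this stands and limits the size of the point. It does not remove the boundary problem, where the report would carry two readings of one result and no guidance.

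Three stronger readings are tempting, and the documents do not support them.

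- A reader might infer that ignoring the stages causes the conflict at 2/50. At 50 evaluable the two-stage limits, 11.6% and 13.2%, also exceed 11.2%.
- A reader might infer that the conflict would persist even with the type I error under 5%. That can be shown at 52 evaluable (25 + 27), where the rule's error is 0.0496, the two-stage one-sided limit 11.18% and the fixed-sample limit 11.62%. The plan sets its rule at 50, where the error is 0.058.
- A reader might infer that the upward-biased crude rate should give way to the UMVUE. The upward bias holds only over all outcomes, including trials stopped at 25. Among trials reaching stage 2 the UMVUE lies further below the truth, and at the boundary it is the more flattering figure.

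It is also fair to say that the evaluable-number issue belongs partly to Section 11.2, and that no section says the cut-off of 2 would be kept at 47. The 0.073 is therefore conditional. It matters here because the inference must be computed at some actual N, and the plan gives no instruction.

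**Conclusion.** The point holds in a limited form. Section 11.4.1 does not specify inference that matches its two-stage design. The direct effect at 2/50 is about half a percentage point on the upper limit (12.1% against 11.6% one-sided, 13.7% against 13.2% two-sided) and 0.071 against 0.058 on the p-value. It is nil at 0/50 and 1/50.

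The visible conflict at 2/50 comes mainly from the rule's type I error of 0.058 against a stated 0.05, and from setting a two-sided 95% interval beside a one-sided rule. Two-stage inference would expose the first cause and the one-sided limit would remove the second, but together they still leave 11.6% above 11.2%.

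The conclusion assumes that the unnamed exact method is Clopper-Pearson and takes 11.2% as the null. The 0.52 chance of reaching 50 evaluable also assumes independent losses.

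**What to change.** Amend Section 11.4.1 before outcome data are reviewed:

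- Keep the crude count and rate as the headline estimate, and name the exact method.
- Add an exact p-value and interval from the two-stage sample space, with stagewise ordering, at the actual stage sizes.
- Report the one-sided 95% upper limit (the upper end of a two-sided 90% interval) beside the decision, with the 95% interval as a supplement.
- State the attained type I error: 0.058 at 50 evaluable, recomputed if the evaluable number differs.
- Optionally add the UMVUE as a secondary estimate. Note that the crude rate is biased upward only over all outcomes, that both estimates run low among trials reaching stage 2, and that the UMVUE is the lower of the two.

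Separately, correct the alpha stated in the Synopsis so that it agrees with the rule.

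The change to Section 11.4.1 costs some SAP wording and a short program, with no added participants. Each extra figure needs a sentence of explanation in the report.
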